### 16 ECONOMIC CONSIDERATIONS

# 16.1 Summary

An economic analysis, adopting the perspective of the NHS, will be conducted in accordance with NICE methods [39], to estimate the cost-effectiveness of the medicines being assessed. The primary economic outcome will be the incremental cost per quality-adjusted life year (QALY) gained, using a trial-based analysis of each "non-futile" intervention over a 12-month time horizon. A health economic analysis plan will be specified, and the economic findings will be reported in accordance with the Consolidated Health Economic Evaluation Reporting Standards (CHEERS) guideline [40].

# 16.2 Data

Primary care consultations, dispensed medicines and secondary care (Accident and Emergency, Admitted Patient Care, Adult Critical Care, Outpatients) resource use will be based on linked Hospital Episode Statistics and electronic primary care data from NHS-Digital and equivalents in the devolved nations. Participant's use of primary care, secondary care, as well as indirect costs (impact on employment), and out of pocket expenses, will also be measured using the core module of ModRUM (the modular resource use measure [41]), administered via the ATOM5 platform. Unit cost data will be obtained from the most recent versions of NHS reference costs [42], the British National Formulary [43], and the annual compendium of unit costs of health and social care [44].

QALYs will be estimated from responses to the EQ-5D-5L, and applying the 3L cross-walk value set [14]. The number of QALYs experienced by each patient will be calculated as the area under the curve, using the trapezoidal rule.

### 16.3 Economic Analysis

Mean total costs and QALYs will be used to calculate the incremental cost-effectiveness ratio. Where appropriate, missing resource use or health outcome data will be imputed [45]. Non-parametric, bootstrapped 95% confidence intervals for items of resource use, costs and QALYs will be estimated (10,000 replicates). Estimates of ICERs will be compared with the NICE £20,000 to £30,000 per QALY threshold of cost-effectiveness, and analyses will be conducted to assess scenarios such as different costing perspective, and the sensitivity of the ICER to changes in parameter estimates. Multivariate sensitivity analyses will be applied where interaction effects are suspected, and the joint uncertainty in costs and benefits will be considered through application of bootstrapping and estimation of cost-effectiveness acceptability curves [46].

In a secondary analysis, a lifetime horizon will be considered using a decision analytic model. Survival curves will be extrapolated using accepted methods [47]; and costs and QALY decrements will be estimated from regression models of trial data, supplemented in the case of QALYs, by population statistics [48]. Costs and benefits accruing after the first year will be discounted at 3.5% per annum.

IRAS ID: 294861 Page **44** of **64** 

### 17 STATISTICAL CONSIDERATIONS

# 17.1 Summary

All analyses for primary and secondary outcomes will be prepared by LCTC and made publicly available within reports, presentations and publications. A more detailed statistical analysis plan [49] developed by the investigators will be available on the study website. The analysis and reporting of the trial will be in accordance with CONSORT guidelines for adaptive designs [50] and CONSORT-PRO [51].

# 17.2 Sample Size

Using a two-sided log-rank test with a significance level of 1% and a hazard ratio of 1.5 implies that 362 events (re-hospitalisation or death) need to be observed to achieve 90% power for a 1:1 allocation ratio comparing a single active treatment vs SoC. Assuming no drop outs and an event rate of 25% [19] in the SoC arm means that a total of 1754 patients (877 per arm) need to be recruited for one comparison. The significance level has been adjusted to allow for multiplicity. The Table below gives the power for this event rate for different assumptions about the true hazard ratio whilst maintaining the required number of events (362). No adjustment for dropouts has been made due to the use of routine data to ascertain events.

Table 1: Power for a 2 treatment comparison when 362 events have been observed for different true outcomes.

	Hazard ratio				
	1.30	1.35	1.40	1.45	1.50
Power (%)	47.0	61.1	73.5	83.2	90.0

# 17.3 Method of Randomisation

# 17.3.1 Allocation Sequence Generation

A randomisation specification document will be written detailing the requirements for the trial according to the Standard Operating Procedures of LCTC. The permuted block randomisation sequence will be generated using STATA version 14 [52]. Allocation ratios will be set to be equal for each trial arm a participant is eligible to be allocated to. Access to the randomisation specification and the allocation sequences generated will be controlled by the LCTC randomisation team.

### 17.3.2 Concealment and Implementation of Allocation Sequence

Patient allocations will be irrevocably generated upon completion of the central randomisation form by a delegated member of the trial research team. Allocation concealment will be ensured as the service will not release the randomisation code until the patient has been recruited into the trial; this takes place after confirmation of eligibility has been completed. Following randomisation, the system will provide the allocation and participant trial identifier sending automated emails of the same for central monitoring purposes.

IRAS ID: 294861 Page **45** of **64** 

# 17.4 Interim Analyses

For each comparison, an interim analysis will be undertaken once 181 events have been observed across both arms in this comparison. A Cox proportional hazards model will be fit on and the treatment effect estimated. If the treatment effect indicates that the active treatment is no better than control (i.e. if the test statistic is zero or worse) the IDSMC may recommend that the study be stopped for futility and recruitment to this treatment will stop. Treatment of all participants already randomised to this comparison will continue until the planned end point to enable meaningful 12 months outcome data to be collected. No early stopping for benefit is planned unless indicated by the Independent Data Monitoring Committee (IDSMC) if the result is likely to convince a broad range of clinicians including participants in the trial and the general clinical community. The IDMC may, at any point, determine there is a safety concern and require a treatment arm to be stopped immediately.

At the interim review point, a sample size re-estimation will be undertaken. The event rate of re-hospitalisation or death will be estimated for the control group and the sample size may be updated on the basis of the new estimate.

Analyses of the accumulating data will be performed at regular intervals (initially at least monthly with frequency under review by the IDSMC) for review by the IDSMC. These analyses will be performed at the LCTC. The IDSMC will be asked to give advice on whether the accumulated data from the trial, together with results from other relevant trials, justifies continuing recruitment of further patients or further follow-up.

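### Sample size re-estimation uses the control-arm event rate, although power rests on 362 events pooled over both arms; the pooled rate would fit that target and disclose less

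*Protocol*

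**What the plan says.** Section 17.2 of the protocol sizes each comparison by events: "362 events (re-hospitalisation or death) need to be observed to achieve 90% power", with a two-sided 1% level, HR 1.5 and 1:1 allocation. It then converts events to patients, "Assuming no drop outs and an event rate of 25% [19] in the SoC arm", and concludes that "a total of 1754 patients (877 per arm) need to be recruited for one comparison". Table 1 in that section varies the true HR while holding the 362 events fixed.

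Section 17.4 states that "an interim analysis will be undertaken once 181 events have been observed across both arms in this comparison". At that look a Cox model estimates the treatment effect for a futility judgement by the IDSMC. At the same point the sample size is reviewed: "The event rate of re-hospitalisation or death will be estimated for the control group and the sample size may be updated". The section does not say how the control rate becomes a new N, whether HR 1.5 is retained, or who is told the rate and its derivation. The interim analyses are done at the LCTC for the IDSMC.

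**The concern.** Two things follow from using one arm's rate in a design driven by pooled events.

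First, the control rate alone cannot say how many patients yield 362 events. It has to be combined with an assumed HR, and the only one that the protocol offers is the design value of 1.5. The result fits the event target only if the true HR is 1.5.

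Second, the interim occurs at a known total of 181 events. With that total fixed, the control rate determines the active rate once the numbers followed are known. A revised N computed from the control rate therefore carries information on the interim treatment effect. The trial is open label and the recruitment target is printed in the protocol overview and in sections 11 and 17.2, so a new target would normally reach the sites. Section 17.6 already values this separation: it reserves SAP changes for a statistician who has not seen comparative data.

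**Working it through.** **Inputs from section 17.2:** two-sided level 1%, power 90%, HR 1.5 (control against active), 1:1 allocation, control event rate 25%, no dropout, 362 events, 1754 patients. **From section 17.4:** look at 181 pooled events. **Assumed, not in the protocol:** proportional hazards, complete and equal follow-up, HR 1.5 kept in the re-estimation, and 400 to 450 patients per arm followed at the interim.

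**1. The plan's own figures.** Events = 4(z₀.₉₉₅ + z₀.₉₀)² / (ln 1.5)² = 362.0, as stated. Power at 362 events is 46.8, 61.0, 73.4, 83.1 and 90.0% for HR 1.30 to 1.50, within 0.2 points of Table 1.

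For patients, the active event probability is 1 − 0.75^(1/1.5) = 0.1745. The mean over the arms is (0.25 + 0.1745)/2 = 0.2123, and N = 362/0.2123 = 1705. Taking the active rate as 0.25/1.5 = 0.1667 gives 1738. Both are within 3% of 1754.

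**2. The two rules compared, true control rate 25%.** The control-rate rule with HR 1.5 kept gives 1705 whatever the true HR. The N that yields 362 events is 362 / {[0.25 + 1 − 0.75^(1/HR)]/2}.

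| True HR | N for 362 events | Control-rate rule | Difference | Events if all 1705 are followed |
|---|---|---|---|---|
| 1.0 | 1448 | 1705 | +17.8% | 426 |
| 1.2 | 1563 | 1705 | +9.1% | 395 |
| 1.3 | 1614 | 1705 | +5.7% | 382 |
| 1.4 | 1662 | 1705 | +2.6% | 372 |
| 1.5 | 1705 | 1705 | 0% | 362 |
| 1.6 | 1746 | 1705 | −2.3% | 354 |
| 1.8 | 1820 | 1705 | −6.3% | 339 |

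The percentages hardly depend on the control rate. For rates of 20% to 35% the excess is 16.7% to 18.3% at HR 1.0 and 5.4% to 5.8% at HR 1.3.

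**3. What the revised N can disclose.** Suppose 181 events among 853 fully followed patients (pooled rate 21.2%). The control-rate rule returns N = 1706, 1803, 1863 and 2016 for an observed HR of 1.5, 1.3, 1.2 and 1.0. The pooled rule returns 362 / (181/853) = 1706 each time.

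Run backwards, a revised N of 1800 implies a control rate of 0.2371. With 425 per arm that is 100.8 control events, 181 − 100.8 = 80.2 active events, and HR = ln(1 − 0.2371) / ln(1 − 80.2/425) = 1.29. With 400 per arm the same N implies 1.12, and with 450 per arm 1.50.

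In simulation with 425 per arm, restricted to runs with 179 to 183 pooled events, the correlation between revised N and interim log HR was −0.99. The relation is tight for someone who knows the denominators and loose for someone who does not.

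**4. Error rate and power.** With N set by the control-rate rule, simulated two-sided type I error stayed at about 0.010. If all 1705 patients are followed, power at HR 1.3 is 49.6% instead of 46.8% at 362 events; at HR 1.6 it is 96.7% instead of 97.1%.

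**The case against.** The strongest reply is that both effects rest on a rule that the protocol does not state. The update is only permitted, not automatic, and the formula may properly sit in the SAP. Updating the control rate under the unchanged design alternative is also consistent with how section 17.2 derived N. This stands as a limit: the percentages hold only if HR 1.5 is kept. But the choice of the control rate as the input is fixed in the protocol itself, and it does not match a pooled event target.

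A reader might infer that the plan unblinds the trial. The documents do not support that. Nothing says that the control rate or its derivation leaves the LCTC and the IDSMC, and the IDSMC sees the treatment effect at that look anyway. Section 10 restricts each comparison to concurrently enrolled, eligible patients, so total platform recruitment does not supply the denominator, and follow-up will be incomplete at the interim. An outsider would get an approximate signal at most.

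A reader might also take the 18% as the expected excess. It arises at an HR of 1.0, which is the boundary of the futility rule. That rule is non-binding, so the case can occur, but about 3% to 9% at HR 1.2 to 1.4 is more realistic. Nor is the surplus wasteful in terms of power, which at 362 events is already below 90% for any HR under 1.5.

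Finally, the control arm is shared, so pooled targets issued for two comparisons could hint at which active arm has fewer events. That is fair, but small: the pooled rate is already implied by when the 181st event occurs, and by itself it does not show active against control.

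**Conclusion.** The point holds as a cheap improvement. Section 17.4 feeds a control-arm rate into a design whose power depends on pooled events. With HR 1.5 retained, the revised N is about 3% too large for 362 events at a true HR of 1.4, 6% at 1.3, 9% at 1.2 and up to 18% at no effect, and 2% to 6% too small at HR 1.6 to 1.8. A published revised N could also give an approximate reading of the interim effect to people outside the IDSMC who know the rule and the numbers followed.

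The consequences are for recruitment, timing and confidentiality of the interim effect. They do not extend to type I error, and the effect on power is slight. The figures assume proportional hazards and complete, equal follow-up; the disclosure figures also assume 400 to 450 patients per arm at the interim.

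**What to change.** In section 17.4, replace the control-group rate with the event probability pooled over both arms of the comparison, estimated by Kaplan-Meier at the planned follow-up horizon because follow-up will be incomplete at the look. State that the 362-event target stays fixed and that N = 362 / pooled probability. Have the calculation produced without arm-level output, and circulate only the resulting target, not the rate or its derivation.

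If the control rate is kept instead, state the rule, including the HR used, and restrict who sees the rate and how N was derived.

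The cost is about one sentence in the protocol, mirrored in the SAP. The remaining downside is the hint between active arms that a shared control allows, which limiting circulation to the target keeps small.

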# 17.5 Adding of arms

New treatments will be added to the platform by recruiting additional participants to the study. When a new potential treatment is to be included in the platform, following regulatory approval of a substantial amendment to the MHRA, it will be added immediately provided that no more than two active treatments currently recruiting to the platform. If the study is already recruiting to three active treatments, then inclusion of a new treatment in the platform will be delayed until one of the current treatment comparisons has reached its recruitment target or has been discontinued for lack of benefit or safety.

# 17.6 Statistical Analysis Plan

A full statistical analysis plan (SAP) will be written prior to the recruitment of the first participant. The SAP will be version controlled and changes to the SAP documented with rationale for the change. Any changes required to the SAP will be implemented by a statistician who has not had access to the trial database or seen comparative summaries of the data accrued to date.

The main features of the SAP are summarised below:

- Analysis will be by the intention to treat principle (ITT)
- Baseline characteristics will be summarized using descriptive statistics only, formal statistical comparisons will not be made
- The primary outcome will be analysed using a Cox proportional hazards model and the assumption of
  proportional hazards investigated. The primary outcome is specified as time to event, with secondary
  interpretation of hospital free survival days. The primary outcome must be interpreted in the light of the

IRAS ID: 294861 Page **46** of **64** 

secondary outcome specified as the number of days alive and out of hospital at 12 months (60 days for purposes of interim analysis).

- Secondary outcomes will be analysed where appropriate using regression models dependent on data type (binary, categorical, continuous etc.)
- Hospital outpatient attendance, speciality and reason, cause specific mortality and reasons for readmission will be summarised as per baseline characteristics
- Any subgroup analyses will be prespecified in the statistical analysis plan in light of accumulating evidence. Pre-specified subgroup analysis of the primary outcome will use the same approach to the analysis
- Point estimates will be reported together with 99% confidence intervals
- As much information as possible will be collected about the reasons for missing outcome data; this will be used to inform any imputation approaches employed in the analysis

IRAS ID: 294861 Page **47** of **64** 

### 18 DATA MANAGEMENT AND TRIAL MONITORING

For the HEAL-COVID trial, the responsibilities for Data Management and monitoring are detailed in separate Data Management and Trial Monitoring Plans. These provide details including the internal processes that will be conducted at the CTU throughout the trial. Justification for the level of monitoring is provided within those documents and the trial-specific risk assessment. All data will be managed as per LCTC processes and in line with all relevant regulatory, ethical and legal obligations.

## **18.1 Source Documents**

The case report form (CRF) will be considered the source document for data where no prior record exists and that is recorded directly in the CRF or Aparito App.

Date(s) of informed consent processes (including date of provision of participant information, randomisation number and the fact that the participant is enrolled in a clinical trial (including possible treatment arms) should be added to the patient's medical record chronologically.

#### 18.2 Data Collection Methods

Data will be collected by using web-based applications, and may include additional paper CRFs. All data will be sent to LCTC where it will be securely stored and used for the purposes of monitoring and final analyses. Data will be collected via the following systems:

- ATOM5 platform (Aparito); an NHS Digital approved, ISO13485, ISO/IEC 27001:2013 Accreditation and FDA CFR21 Part 11 compliant digital data collection platform designed specifically for clinical trials. Trial participants will be able to submit data via smart phone or web-portal, and data entry will be possible in multiple languages. A dedicated Aparito team member will be available via telephone to assist trial participants with any technical issues they experience with the platform or entering their data. Given the age profile of patients admitted to hospital with COVID-19, consideration has been given to their likely preference/ability for submitting patient reported data via smartphone/website. Patients or their proxy who do not have access to/cannot use a smartphone or internet, will be contacted by a member of the core study research team to determine their preference of format in which they wish to submit patient-reported data (written or via telephone interview), and will be supported to do so in the chosen manner.
- NHS Digital and the equivalent bodies in the devolved nations. Patients' randomisation numbers, NHS numbers/CHI numbers, DOBs, randomisation dates and end of participation dates will be sent to NHS Digital (English data), Public Health Scotland's electronic Data Research and Innovation Service (eDRIS) (Scottish data), and the Secure Anonymised Information Linkage (SAIL) databank (Welsh data), where they will be linked with routine healthcare data regarding mortality and hospital readmissions. The NHS/CHI numbers will then be removed, and the linked data will be securely transferred to the LCTC for storage and analysis.

As there is no equivalent to NHS Digital in Northern Ireland, Northern Ireland sites will provide critical routine healthcare data directly to LCTC.

• **Public Health Scotland Safe Haven.** At the end of the trial, the data from HEAL-COVID will be stored in the PHS National Safe Haven to allow data linkage with other COVID trials.

IRAS ID: 294861 Page **48** of **64** 

• Randomisation information will be held within the trial specific randomisation system at LCTC. All routine medical data collected will be stored within a password protected study specific database with audit trail functionality. Delegated LCTC staff will only have access to view data in order to perform monitoring and analysis. Any data transfers will be undertaken using secure methods. Additional detail will be outlined in the Data Management Plan.

# 18.3 Monitoring

Monitoring is conducted to ensure protection of the participants within the trial, and that all aspects of the trial (procedures, laboratory, trial intervention administration and data collection) are of high quality and conducted in accordance with Sponsor and regulatory requirements.

A detailed Trial Monitoring Plan will be developed and agreed by the TMG and CI to describe who will conduct the monitoring, the frequency, and what level of detail monitoring will be conducted. Monitoring will be dependent on the documented risk assessment of the trial, which determines the level and type of monitoring required for specific hazards. All processes may be subject to monitoring, e.g. enrolment, consent, adherence to trial interventions, accuracy and timeliness of data collection etc.

Trial Oversight Committees related to the monitoring of the trial are detailed in Roles and Responsibilities see section 7.

## 18.3.1 Central Monitoring

There are a number of monitoring features in place at the CTU to ensure reliability and validity of the trial data, to be detailed in the Trial Monitoring Plan. Data will be checked for missing or unusual values (range checks) and for consistency within participants over time. Other data checks relevant to participant rights and safety will also be regularly performed as per CTU processes. Any suspect data will be queried with sites within the trial database. Individual sites will respond to the queries providing an explanation/resolution to the discrepancies and update the data in the database (where appropriate).

It is noted that there will be limited opportunity for resolution of data queries due to time frames and site capacity. Therefore, all systems used to capture data will have data validations built in to raise warnings at the point of data entry. Any additional data cleaning will be restricted to key data items pertaining to safety and primary outcome.

Site monitoring visits may be 'triggered' in response to concerns regarding study conduct, participant recruitment, outlier data or other factors as appropriate.

### 18.3.2 Clinical Site Monitoring

All monitoring within HEAL-COVID will be done remotely.

#### 18.4 Risk Assessment

A full and comprehensive risk assessment will be conducted for HEAL-COVID with a monitoring plan developed appropriate to risks identified. Given the adaptive nature of the trial the risk assessment will be reviewed following removal or addition of trial interventions.

IRAS ID: 294861 Page **49** of **64** 

